#### **10.6.5 Administrative and Regulatory Requirements**

This is an investigator-initiated study. The Study Chair and sponsor-investigator, [name], is conducting the study and acting as the sponsor. Therefore, the legal/ethical obligations of the Study Chair include both those of a sponsor and those of a principal investigator.

#### **10.6.6 Auditing and Monitoring:**

The Vanderbilt-Ingram Cancer Center (VICC) oversees patient safety and data monitoring for its investigator-initiated and NIH-NCI funded clinical trials through its Data and Safety Monitoring Committee (DSMC). The purpose of the DSMC is to ensure the efficient implementation and management of the VICC Data and Safety Monitoring Plan (DSMP). The Committee maintains authority to intervene in the conduct of studies as necessary to ensure clinical research performed at VICC achieves the highest quality standards.

The VICC DSMC meets on a quarterly basis and ad hoc to discuss data and safety monitoring of clinical trials and to oversee the VICC DSMP. Internal audits for compliance with adverse event reporting, regulatory and study requirements, and data accuracy and completion are conducted according to the VICC DSMP according to study phase and risk. The committee reviews all serious adverse events (SAE) on Vanderbilt sponsored investigator-initiated studies on a quarterly basis and provides DSMC SAE review reports to the Vanderbilt IRB.

The trial additionally will be monitored by the VICC Multi-Institutional Coordinating Center. The actual frequency of monitoring will depend on the enrollment rate and performance of the site. Monitoring will be conducted through onsite and/or remote monitoring, teleconferences with the Investigator and site staff, and appropriate communications by mail, fax, email, or telephone. The purpose of monitoring is to ensure that the study is conducted in compliance with the protocol, standard operating procedures (SOPs), and other written instructions, and to ensure the quality and integrity of the data.

During scheduled monitoring visits, investigators and the investigational site staff must be available to discuss the progress of the trial, make necessary corrections to case report form entries, respond to data clarification requests, provide required regulatory documents, and respond to any other trial-related inquiries of the monitor.

In addition to the above, the FDA may review the conduct or results of the study at the investigational site.

### **10.6.7 Data Handling and Record Keeping**

An electronic case report form (eCRF) is required and must be completed for each included participant. The completed dataset should not be made available in any form to third parties, except for authorized representatives of appropriate Health/Regulatory Authorities, without written permission from Vanderbilt.

To enable evaluations and/or audits from health authorities and Vanderbilt, each site investigator agrees to keep records including: The identity of all participants (sufficient information to link records; e.g., hospital records), all original signed informed consent forms, copies of all source documents, and detailed records of drug disposition. To comply with international regulations, the records should be retained by the investigator in compliance with regulations.

Queries resulting from review of the eCRFs will be generated for the site and corrections will be made by the study site personnel. This will be done on an ongoing basis.

### **10.6.8 Data Verification**

Data will be collected via eCRFs and entered into the database per Coordinating Center guidelines. The Coordinating Center will check data accuracy by performing source data verification. Source data verification is a direct comparison of the entries made on the CRFs against the appropriate source documentation. This will be conducted remotely, with the possibility of on-site verification periodically. Discrepancies in the data will be brought to the attention of the investigator and/or the investigator's staff. Any necessary corrections will be made directly to the eCRFs or via queries by the investigator and/or the investigator's staff.

### **10.6.9 Study Closure**

The Coordinating Center reserves the right to discontinue a site at any time during the study for medical or administrative reasons such as:

- Unsatisfactory enrollment;
- GCP noncompliance;
- Inaccurate or incomplete data collection;
- Falsification of records;
- Failure to adhere to the study protocol.

### **10.6.10 Protocol Deviations**

The Coordinating Center is responsible for implementing and maintaining quality assurance and quality control to ensure that studies are conducted according to the protocol, GCP, and all applicable regulatory requirements. A protocol deviation is any noncompliance with the protocol. Noncompliance can be on the part of the study participant, the investigator, or the study site staff. Deviations to the protocol are not permitted except when necessary to eliminate an immediate hazard to study subjects.

### 10.6.11 Changes to Protocol and Informed Consent Document

Any change to the protocol or informed consent document must be reviewed and approved by the Coordinating Center before being submitted to the Institutional Review Board/Independent Ethics Committee at participating institutions. Amendments should not be implemented until all necessary approvals have been obtained, except when necessary to eliminate an immediate hazard to study subjects.

## **APPENDIX 1: EXCLUDED AND CAUTIONARY MEDICATIONS AND DIETARY RESTRICTIONS**

Excluded throughout the study:

• Grapefruit and grapefruit products.

• Seville Oranges (including marmalade containing Seville oranges)

• Starfruit.

• Concurrent therapy with any other approved or investigative anticancer therapeutics.

• Other investigational agents.

Excluded during venetoclax ramp-up phase; and Cautionary when receiving venetoclax at the steady state dose:

• Strong CYP3A inhibitors.

• Strong CYP3A inducers.

• Moderate CYP3A inhibitors

— Exclude during the first cycle and consider alternative medications.

— If a subject requires use of these medications at the venetoclax plateau dose, use with caution and reduce the venetoclax dose by 50% for moderate inhibitors. After discontinuation of a moderate CYP3A inhibitor, wait for 3 days before the venetoclax dose is increased back to the initial target dose.

• Moderate CYP3A inducers

— Exclude during the ramp-up phase and consider alternative medications.

Cautionary throughout the study:

• Warfarin (closely monitor the international normalized ratio, INR).

• P-gp substrates

• BCRP substrates

• OATP1B1/1B3 substrates

• P-gp inhibitors

• BCRP inhibitors

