### Medications:

Venetoclax should not be used with strong CYP3A inhibitors (e.g., ketoconazole, ritonavir, clarithromycin, itraconazole, voriconazole) at initiation, during ramp-up, and pre-remission phase of treatment. Concomitant use of venetoclax with moderate CYP3A inhibitors (e.g. erythromycin, ciprofloxacin, diltiazem, fluconazole, isavuconazole, verapamil), or strong CYP3A inducers (e.g. carbamazepine, phenytoin, rifampin, St. John's wort), or moderate CYP3A inducers (e.g. bosentan, efavirenz, etavirine) may be used, if clinically appropriate, during the post-remission phase with appropriate dose adjustments. See [Table 8](#) and [Appendix 1](#) for a list of representative products.

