### 5.3.1 Antifungal prophylaxis

Prophylactic antifungal therapy with CYP3A4 inhibitor activity (eg, fluconazole, posaconazole, and voriconazole) are prohibited 7 days or 5 half-lives, whichever is greater, prior to C1D1 and through the pre-remission phase of therapy. Alternative antifungal therapy should be considered per institutional guidelines. During subsequent cycles, investigators may use prophylactic antifungal therapy as guided per local institutional practices. If the therapy of choice is a drug with CYP3A4 inhibitor activity, dose adjustments of venetoclax are required as detailed in [Table 8](#).

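### Sections 5.3 and 5.3.1 keep strong CYP3A inhibitors and CYP3A4-inhibiting antifungal prophylaxis out of the whole pre-remission phase, but Appendix 1 excludes strong inhibitors only during ramp-up

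*Combined protocol and SAP*

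**What the plan says.** **Strong inhibitors.** The medications paragraph of Section 5.3 rules them out "at initiation, during ramp-up, and pre-remission phase of treatment". Appendix 1 places them under the heading "Excluded during venetoclax ramp-up phase; and Cautionary when receiving venetoclax at the steady state dose", and their bullet adds no further limit.

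**Antifungal prophylaxis.** Section 5.3.1 names fluconazole, posaconazole and voriconazole as examples of prophylaxis with CYP3A4 inhibitor activity. It says such drugs "are prohibited 7 days or 5 half-lives, whichever is greater, prior to C1D1 and through the pre-remission phase of therapy". Appendix 1 has no matching entry.

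**Moderate inhibitors.** Section 5.3 says these, together with strong and moderate inducers, "may be used, if clinically appropriate, during the post-remission phase with appropriate dose adjustments". Appendix 1 lists moderate inhibitors under the ramp-up heading above, but their own bullet reads "Exclude during the first cycle and consider alternative medications". It then continues: "If a subject requires use of these medications at the venetoclax plateau dose, use with caution", with a venetoclax reduction.

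**Standing of the appendix.** Section 5.2.11 lets patients stay on baseline medication unless the eligibility criteria or Appendix 1 prohibit it. Section 5.3 also refers to Appendix 1, though for a list of products rather than for timing. No passage says which text prevails.

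**The concern.** A site deciding whether a pre-remission patient may take a strong CYP3A inhibitor gets one answer from Section 5.3 and another from Appendix 1. The question will arise. Section 5.2.6.1 calls for prompt anti-infective treatment, including antifungals, in patients with fever or signs of systemic infection, and its restart guidance covers patients not yet in remission. Section 5.3.1 governs prophylaxis only, so a site considering a therapeutic azole with strong inhibitor activity is left with the two texts that disagree.

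Two things are at stake. The first is patient safety. The second is whether patients at the same nominal dose level are comparable while DLTs are being counted. Table 4 decides on very few patients: 0 of 3 proceeds, 1 of 3 adds three more, and 2 or more of 3 or of 6 moves to the next lower level. Table 10 sets its first boundary at 2 DLTs in 6 patients. One patient whose venetoclax exposure differs because of an interacting drug could tip such a decision.

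**Working it through.** There is no statistical figure to reproduce. The check sets the windows side by side and counts days.

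**Inputs**
- Ramp-up: days 1 and 2 of Cycle 1, with the steady dose from day 3 (Section 5.2.1.1; Table 5 footnote).
- Cycle length: 28 days (Section 5.2.2).
- Pre-remission phase: one cycle, or two if the C1D22 marrow is involved (Section 7.4).
- DLT window: to day 28 (Section 5.2.4).
- Table 8 venetoclax doses: 400 mg with no interacting drug, 100 mg with strong inhibitors other than posaconazole, and 70 mg with posaconazole.

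**Windows compared**

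| Class | Sections 5.3 and 5.3.1 | Appendix 1 | Days in conflict |
|---|---|---|---|
| Strong inhibitors | Expressly barred through pre-remission | Excluded in ramp-up, then cautionary | Day 3 onward |
| Antifungal prophylaxis with CYP3A4 inhibitor activity | Expressly barred through pre-remission | No separate entry; follows inhibitor class | As for its class |
| Moderate inhibitors | Use placed in post-remission, so barred earlier by implication | Heading: ramp-up; bullet: first cycle | Bullet: Cycle 2; heading: day 3 onward |

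**Day counts**
- Strong inhibitors, one pre-remission cycle: 28 − 2 = 26 days, all inside the DLT window.
- Strong inhibitors, two pre-remission cycles: (2 × 28) − 2 = 54 days.
- Moderate inhibitors, on the bullet: 56 − 28 = 28 days, all in pre-remission Cycle 2 and none inside the 28-day DLT window.

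These are the longest periods over which the texts can disagree. They are not expected exposure times, and the documents do not say how many patients would take such a drug.

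**Indirect indication of size**
- 400 / 100 = 4.0
- 400 / 70 = 5.7

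These are ratios of doses, not of exposures. They show that the protocol treats the interaction as large, but they do not measure it.

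**Inducers.** A similar mismatch exists. Section 5.3 places strong and moderate inducers in the post-remission phase, while Appendix 1 excludes both only during ramp-up.

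**The case against.** The best reply is that the texts can be read cumulatively: the stricter rule in Sections 5.3 and 5.3.1 binds every patient, and the appendix only adds to it. Exclusion criterion 10 also keeps out patients on non-permitted medication at entry. A reader might therefore resist the inference that Appendix 1 gives free permission for strong inhibitors from C1D3, and that resistance is fair. Cautionary is not unrestricted, and Section 5.3 applies to the same patient. But nothing in the protocol states the cumulative reading or an order of precedence, so the contradiction stands.

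The second reply is that dose adjustment would offset the interaction. Section 5.2.6.1 says venetoclax should be adjusted for drug interactions, and its guidance includes patients before remission; the Table 8 title names no phase. This has weight. It also defeats the inference that a patient would receive four to six times the intended exposure, which would need an uncorrected interaction of a size the documents never state. The reply is incomplete, though. Section 5.3 ties adjustment to the post-remission phase and Section 5.3.1 to subsequent cycles, while Appendix 1 gives no reduction for strong inhibitors.

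Third, evaluability is not wholly open. Section 5.2.4 says a dose reduction in the DLT period is not itself a DLT if the minimum doses at the prescribed level are taken, and Section 5.2.6.3 says Cycle 1 reductions are to be avoided in dose finding. What these leave unaddressed is a patient taking an inhibitor with no reduction. That is missing detail, separate from the contradiction.

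Finally, a reader might infer that Section 5.3 expressly bars every CYP3A inhibitor before remission. It does so only for strong ones.

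**Conclusion.** The contradiction is explicit for strong CYP3A inhibitors, and for antifungal prophylaxis wherever the agent is a strong inhibitor. It runs from C1D3 and covers up to 26 of the 28 DLT-window days. For moderate inhibitors it is weaker. The earlier bar in Section 5.3 is implied, with an express bar only for antifungal prophylaxis, and Appendix 1 disagrees with itself between heading and bullet. On the bullet, the moderate-inhibitor conflict lies in pre-remission Cycle 2 and does not touch the 28-day DLT window.

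Different site practice could give different venetoclax exposure at one dose level and so could affect DLT counts. It would go too far to say that the DLT count or the recommended phase 2 dose is confounded. That depends on how many patients take such drugs, which passage their site follows and whether doses are adjusted, none of which the documents settle.

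The conclusion assumes that ramp-up means days 1-2, as Section 5.2.1.1 sets it, and that Appendix 1 is operative, as Section 5.2.11 indicates. It is an internal inconsistency that should be corrected.

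**What to change.** The sponsor must reconcile Section 5.3, Section 5.3.1, Table 8 and Appendix 1 so that each drug class (strong inhibitors, moderate inhibitors, strong and moderate inducers, antifungal prophylaxis) has one exclusion period, worded alike wherever it appears. The heading and the moderate-inhibitor bullet in Appendix 1 need to agree. The same edit should say in which phases the Table 8 adjustments apply, so that Section 5.2.6.1 and Sections 5.3 and 5.3.1 no longer point to different periods. Which period or adjustment is right is for the sponsor's clinical team; none is proposed here.

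While amending, it would help to add a sentence on how a patient who takes an excluded inhibitor inside the DLT window is classed for evaluability.

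The cost is a wording amendment, with study chair approval and IRB approval at each participating centre. Sample size, decision boundaries and analysis are unchanged.
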